To date, the majority of randomized controlled trials (RCTs) have used rest and psychological approaches to alleviate persistent concussion symptoms and have focused on providing individuals with recovery-related information, reassurance, or education. Most of these studies have found no benefit or reported inconclusive findings¹⁰. Of the research that has focused on treatment, AET¹¹ has shown to be promising for overall symptom reduction. The conclusions of these studies, however, are limited by the lack of control groups, biased samples, and the inclusion of TBIs of all severities. In addition, many of the interventions were delivered prior to the period when symptoms are typically considered persistent. Controlled studies are needed to test the specific effects of treatment on the persistent symptoms in a post-concussion syndrome sample lasting greater than one month post-concussion. The intervention we plan to test is AET in a controlled/stepwise exercise training program using RCT methodology. Recent evidence indicates that an active rehabilitation program may be useful for individuals with persistent concussion symptoms¹² and that exercise can also be effective at improving mood¹³.

Studies have also shown that levels of brain-derived neurotrophic factor (BDNF) are significantly increased as a result of aerobic exercise in healthy individuals. In particular, preliminary data from our group¹⁴ demonstrated an increase in salivary BDNF levels in a healthy control group following 4 weeks of AET (the same protocol we are proposing). BDNF is a secreted protein that has been shown to play a central role for neural health and brain plasticity^{15,16}. BDNF has been demonstrated to be a useful biomarker of brain injury post-concussion¹⁷ with animal research showing significantly reduced levels of BDNF several hours or days after a concussion¹⁸. Notably, aerobic fitness and BDNF share a relationship that is predictive of memory performance in healthy individuals¹⁹⁻²¹. Also, it is known that executive function and circulating BDNF both decline with age, however, changes in serum BDNF

predicts improvements in cognitive outcomes in response to aerobic exercise in older individuals²².

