4.2 Study Sample Description

For the experimental group, the population being evaluate is anyone age 18-50 years, at least two weeks post injury, experiencing at least one PCS symptom that is mild in severity, as well as the remaining inclusion criteria (see attached screening checklist, Section 16.3). For the healthy control group, the population being evaluated is anyone age 18-50 years, as well as the remaining inclusion criteria (see attached screening checklist, Section 16.3)

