4.4 Participant Inclusion Criteria

A participant is eligible for inclusion in the study if the individual meets all of the following criteria:

1. Man or woman aged 18-50 years.

2. Reports at least one PCS symptom that is mild in severity.
3. It has been between two weeks and six months since date of injury.
4. Is able to provide consent in English

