5. STUDY DESIGN

5.1 Study Design

This study is designed as a randomized controlled trial. Potential PCS participants will be referred to another member of the research team by [name]. Potential participants will then complete the informed consent process and pre screening checklist. Potential healthy participants will contact the research team directly and set up a time to complete the informed consent, pre screening process, and IPAQ. After being deemed eligible based on the screening criteria (screening checklist attached, section), PCS participants will be randomly assigned to either an AET or standard of care (SC) intervention (see section 7). Using minimization software, each intervention group will be balanced by age and sex. Healthy participants will serve as the control group (HC) and will receive no treatment. Once participants in the SC group have completed the study, the AET will be offered, although it will not be included in the data analysis. Following informed consent, PCS participants will be provided with Garmin VivoSmart HR unit to monitor aerobic activity outside of the study (accelerometer, heart rate monitor, and step counter capabilities). Participants will be required to wear the Garmin units as often as possible for the duration of the study. In place of the Garmin VivoSmart HR unit, participants in the HC group will complete the IPAQ to determine physical activity levels prior to participating in the study,.

All participants will compete a series of pre and post intervention assessments (see section 7.2) over the course of one week at Lakehead University. Following the pre intervention assessments,

participants in the AET group will complete an eight week aerobic and balance retraining program at the School of Kinesiology, Lakehead University (see section 7.2). Participants in the SC group will continue with his/her standard of care for eight weeks. Healthy participants will be instructed not to significantly change his/her lifestyle (diet, physical activity) for the duration of the study weeks. After eight weeks, all participants will complete the assessments once again.

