16. APPENDICES

16.1 Recruitment materials

Do you have symptoms related to a concussion?

Help local researchers examine the effects of exercise on persistent symptoms

Who can participate?

- Adults between 18 and 50 years
- Fluent in English
- No history of neurological disorder
- 2 weeks to 6 months since injury
- Drivers license
- Not currently seeking counselling/therapy for depression

Contact us for more information!

[contact]

[name]
Assistant Professor
Lakehead University

For more Information about your rights as a research participant, contact the TBRHSC Ethics Board Chair at [name]

Are you a healthy individual with no concussion symptoms?

Help local researchers examine the effects of exercise on persistent symptoms

Who can participate?

- Adults between 18 and 50 years
- Fluent in English
- No history of neurological disorder
- Drivers license
- Not currently seeking counselling/therapy for depression

Contact us for more information!

[contact]

[name]
Assistant Professor
Lakehead University

For more Information about your rights as a research participant, contact the TBRHSC Ethics Board Chair at [name]

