16.2 Informed consent materials

16.3 Screening checklists

Inclusion/Exclusion Criteria Screening Checklist- PCS

Participant number _____

- Person aged 18-50 years
- Fluent in English
- Experience injury greater than 2 weeks ago?
- Experienced injury less than 6 months ago?
- Not diagnosed with psychological/neurological disorder
- Not diagnosed with depression
- Not currently seeking counselling/therapy for depression
- Has valid drivers license with 12 months driving experience

Inclusion/Exclusion Criteria Screening Checklist- HC

Participant number _____

- Person aged 18-50 years
- Fluent in English
- Not diagnosed with psychological/neurological disorder
- Not diagnosed with depression
- Not currently seeking counselling/therapy for depression
- Has valid drivers license with 12 months driving experience

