16.4 Data abstraction form

Participant Number: _____

Consent Date:

| | |
|--------------------------|--|
| Sex (male/female) | |
| Height (cm) | |
| Weight (kg) | |
| Age (in years) | |
| | |
| Date of injury | |
| Date of first assessment | |

Past Medical History

- Concussion
- Traumatic brain injury
- Migraine
- ADHD
- Motion sickness

(Y/N)

| |
|--|
| |
| |
| |
| |
| |

How many?

| |
|--|
| |
|--|

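### Entry opens at two weeks although the rationale calls for a sample beyond one month, and the recorded time since injury is neither balanced nor adjusted for: this costs precision in AET vs SC and leaves the three-group and pre-post analyses open to natural recovery.

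*Combined protocol and SAP*

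**What the plan says.** **Target population.** Section 1 criticises earlier work because "many of the interventions were delivered prior to the period when symptoms are typically considered persistent". It then says controlled studies are needed "in a post-concussion syndrome sample lasting greater than one month post-concussion". The primary objective in section 2 is to reduce persistent symptoms.

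**Entry window.** Section 4.4: "It has been between two weeks and six months since date of injury". Section 4.2: "at least two weeks post injury", with no upper limit given there. Flyer in 16.1: "2 weeks to 6 months since injury". PCS checklist in 16.3: "Experience injury greater than 2 weeks ago", followed by a six-month upper limit. No section explains why entry opens before one month.

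**Allocation.** PCS participants are randomised to AET or SC by minimisation, and "each intervention group will be balanced by age and sex" (5.1). Section 6.4 names the same two factors. Healthy controls (HC) are not randomised.

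**Analysis.** Section 11.2 sets a mixed ANOVA with three groups and two times and no covariate. If there is no interaction, it falls back on the main effects of time and group. Section 10 describes the main analysis as a comparison of outcomes before and after.

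**Data.** The abstraction form in 16.4 has a field for "Date of injury" and another for the date of the first assessment. No analysis uses the interval between them.

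**The concern.** There are two linked problems. First, the rationale and the eligibility criteria describe different populations. Some participants will enter before the point at which the protocol's own rationale treats symptoms as persistent, so a conclusion about persistent symptoms would not rest wholly on the sample that section 1 calls for.

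Second, six months is about 13 times two weeks (182/14), and time since injury may well predict how much a participant improves unaided over eight weeks. Leaving it out of both allocation and model gives up precision in a small trial and leaves chance imbalance uncorrected. Separately, several planned analyses do not isolate AET vs SC, and in those, ordinary recovery could be read as an effect of exercise.

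**Working it through.** The plan gives no entry distribution, recovery rate or correlation, so there is no stated figure to reproduce. Everything below is an illustration under stated assumptions.

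**Inputs from the protocol:** window of two weeks to six months (4.4), taken as 14 to 182 days; 20 per arm (5.2, 11.1); one month taken as 30 days.

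**1. Uniform entry (assumption)**
- SD = (182 - 14)/√12 = 168/3.464 = 48.5 days.
- SE of the AET-SC difference in means = 48.5 × √(2/20) = 15.3 days.
- P(|difference| ≥ 14 days) = 2 × [1 - Φ(14/15.3)] = 0.36.
- Share entering before one month = (30 - 14)/168 = 9.5%.

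**2. Early clustering (assumption: exponential from day 14, truncated at day 182)**

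| Scale (days) | Entering before day 30 | SD (days) | SE of difference (days) | P(gap ≥ 14 days) |
|---|---|---|---|---|
| 30 | 41% | 28 | 8.9 | 12% |
| 45 | 31% | 36 | 11.5 | 22% |
| 60 | 25% | 41 | 12.9 | 28% |

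The two scenarios must be read separately: the case with most early entrants has the smallest chance of a 14-day gap, and the reverse.

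**3. Precision from adjustment.** If the partial correlation of time since injury with outcome, given the other covariates, is r (assumed 0.3 to 0.5), adjustment removes r² of the residual variance: 0.3² = 9% to 0.5² = 25%. Ignoring the degrees of freedom spent, 20 per arm then works like 20/0.91 = 22 to 20/0.75 = 27.

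**4. Where natural recovery can mislead.** Simulation with no AET effect, 20 per group, uniform entry, equal natural recovery in AET and SC that fades with time since injury (exponential, six-week constant) and none in HC. Recovery is the mean in SDs of change; 5% is nominal.

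| Test | Recovery 0.25 | 0.5 | 0.8 |
|---|---|---|---|
| AET vs SC | 4% | 5% | 5% |
| Three-group interaction | 10% | 28% | 57% |
| AET pre-post | 16% | 46% | 76% |

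With entry from one month and the same recovery curve, the interaction rejects in 8%, 19% and 38% of trials and the pre-post test in 14%, 32% and 60%. The window contributes, but moving it would not remove the problem. The time main effect was not simulated; it is exposed for the same reason, since it averages recovery over groups.

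**5. Conditional error in AET vs SC.** In the roughly 3% of simulated trials where AET participants happened to enter at least four weeks earlier than SC, the spurious advantage was about 0.33 SD (recovery 0.5) or 0.54 SD (recovery 0.8), and favourable false positives were 14% or 25% instead of 2.5%.

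**6. Gain from minimising on a one-month split.** Under uniform entry the stratum means are 22 and 106 days. Between-stratum variance = 0.0952 × 0.9048 × 84² = 608, against a total of 48.5² = 2,352, or 26%. Perfect balance would cut the SE from 15.3 to 15.3 × √0.74 = 13.2 days and the 14-day chance from 36% to 29%.

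**The case against.** The strongest objection is that SC is randomised and concurrent. Both PCS arms recover naturally, and chance imbalance in an unstratified factor is already allowed for in the type I error of the test. That stands. A reader might infer that the wide window and missing covariate bias AET vs SC, so that recovery passes for treatment effect in that contrast. The design does not support this: in the simulation the average bias is about zero and the rejection rate stays at 4-5%. What survives is lost precision and the conditional error in an imbalanced trial.

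A reader might also infer that the trial simply repeats the fault it finds in earlier work. That goes too far. The criticism concerns when treatment was delivered. Here a week of baseline assessment follows randomisation (7.2) and AET runs for eight weeks, so a day-14 entrant would start at about day 21 and receive most sessions after one month. Allowing seven days, about 5% of entrants under uniform entry, (23 - 14)/168, would start before day 30, or 15-26% under early clustering. Section 1 also describes a gap in the literature, while section 4.2 states the study population as two weeks or more. The mismatch still needs an explanation, because the objective and the conclusions are framed around persistent symptoms.

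Finally, a covariate cannot just be added to the model in 11.2, because HC participants have no injury date. That is correct, and it shapes the fix.

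**Conclusion.** The point holds in three parts.

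- **Text conflict (certain).** Section 1 and sections 4.2, 4.4, 16.1 and 16.3 disagree about the lower bound and must be reconciled. Between about 10% (uniform entry) and 25-41% (early clustering) of participants would enter before one month.
- **AET vs SC (efficiency, not bias).** The comparison is unbiased on average with nominal type I error. Leaving out time since injury forgoes 9-25% of residual variance if the partial correlation is 0.3-0.5. It also leaves a 36% chance (uniform) or 12-28% chance (early clustering) of a gap of 14 days or more.
- **Other planned analyses (exposed to natural recovery).** The three-group interaction with non-randomised controls, the time main-effect fallback and the pre-post comparison can each reflect recovery alone. Under the assumed recovery of 0.25-0.8 SD, the interaction gave 10-57% and the pre-post test 16-76% false positives.

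The entry distributions, correlations and recovery sizes are all assumptions. The text conflict and the omission from allocation and model are not.

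**What to change.** 1. **Reconcile the population.** Either align section 1 with 4.2, 4.4, 16.1 and 16.3, or pre-specify an analysis of participants more than one month post-injury and limit claims about persistent symptoms to it. Raising the lower bound would narrow recruitment; the pre-specified analysis would not, but it would be smaller.
2. **Section 11.2.** Make the primary contrast a two-arm AET-vs-SC ANCOVA of the post value, adjusted for baseline value, days from injury to baseline, age and sex. This is a separate model, not an extra term in the three-group ANOVA. It costs four degrees of freedom (residual 38 to 34 with 20 per arm) and uses data already collected.
3. **Healthy controls.** Keep HC as a descriptive reference only, since the injury-date covariate is undefined for them.
4. **Sections 10 and 11.2.** State that efficacy will not be concluded from within-group pre-post changes or time main effects.
5. **Optional, only if randomisation has not started.** Add time since injury as a QMinim factor. A one-month split alone brings a modest gain in balance (36% to 29% under uniform entry), so it supplements the covariate and does not replace it.

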4.5 Participant Exclusion Criteria

A participant is ineligible for the study if the individual meets any of the following criteria

1. Has been previously diagnosed with a psychological/neurological disorder
2. Has been previously diagnosed with a substance abuse disorder/impairment,
3. Is currently seeking therapy/counselling for depression,
4. Does not have valid driver's license and 12 months of driving experience.

4.6 Participant Withdrawal Criteria

Withdrawal will occur upon participant request. A participant who wishes to withdraw consent from the study will be asked to specify if he/she wish for any data or samples collected to be withdrawn from the study. Samples and data will be withdrawn in accordance with the participant's wishes.

5. STUDY DESIGN

5.1 Study Design

This study is designed as a randomized controlled trial. Potential PCS participants will be referred to another member of the research team by [name]. Potential participants will then complete the informed consent process and pre screening checklist. Potential healthy participants will contact the research team directly and set up a time to complete the informed consent, pre screening process, and IPAQ. After being deemed eligible based on the screening criteria (screening checklist attached, section), PCS participants will be randomly assigned to either an AET or standard of care (SC) intervention (see section 7). Using minimization software, each intervention group will be balanced by age and sex. Healthy participants will serve as the control group (HC) and will receive no treatment. Once participants in the SC group have completed the study, the AET will be offered, although it will not be included in the data analysis. Following informed consent, PCS participants will be provided with Garmin VivoSmart HR unit to monitor aerobic activity outside of the study (accelerometer, heart rate monitor, and step counter capabilities). Participants will be required to wear the Garmin units as often as possible for the duration of the study. In place of the Garmin VivoSmart HR unit, participants in the HC group will complete the IPAQ to determine physical activity levels prior to participating in the study,.

All participants will compete a series of pre and post intervention assessments (see section 7.2) over the course of one week at Lakehead University. Following the pre intervention assessments,

participants in the AET group will complete an eight week aerobic and balance retraining program at the School of Kinesiology, Lakehead University (see section 7.2). Participants in the SC group will continue with his/her standard of care for eight weeks. Healthy participants will be instructed not to significantly change his/her lifestyle (diet, physical activity) for the duration of the study weeks. After eight weeks, all participants will complete the assessments once again.

5.2 Number of Participants/Assignment to Treatment Groups

It is anticipated that 60 participants will be recruited into this study. Participant enrollment will be split between the AET, SC, and HC group. There will be 20 participants in each group.

5.3 Duration of Study and Study Timeline

The study is expected to last one year in total following the coordination of the research team and ethics approvals. Note: These dates are subject to change based on the date we begin participant recruitment. The relative timeline will remain the same.

| Timeline | Milestone Targets |
|----------------------|---|
| Sept 2017 - Dec 2017 | Obtain ethics approval Coordinate research team |
| March- Dec 2019 | Project start date (March 2018) Recruitment, intervention, data collection |
| Oct 2019- Dec 2019 | Data analysis |
| Feb 2020 | Manuscript completion Conference presentations |

5.4 Length of Participation

Participation in this study will last 10 weeks, depending on scheduling of the pre and post intervention assessments. Pre intervention assessments will be conducted at Lakehead University before beginning intervention. The AET intervention will occur three times per week for eight weeks. Each session will last approximately one hour. The SC intervention will be ongoing throughout the eight weeks. The HC group will not complete an intervention. Final assessments will be completed after any intervention has concluded.

6. PARTICIPANT ENROLLMENT

6.1 Participant Identification and Recruitment Procedures

The recruitment will include the use of flyers (attached, Section 16.1) and social media. Recruitment flyers directed at potential participants with PCS will be placed in [name] office at Fairway Physiotherapy, as well as other healthcare clinics around Thunder Bay. In order to recruit healthy participants, and to reach the general public, the research team will post the recruitment poster on the Lakehead University School of Kinesiology Facebook page and Twitter page. Posters will also be displayed around Lakehead University and various public spaces around Thunder Bay. If a potential PCS participant expressed interest in participating,

he/she will be referred by his/her healthcare provider, or referred by his/her self to [name], who will forward his/her information to the research team if appropriate. If a potential healthy participant is interested in participating, he/she will contact the research team using the contact information on the recruitment posters. An appointment will be set up between he/she and a member of the research team at the Lakehead University School of Kinesiology.

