11.2 Statistical Analysis

The main analysis will be a mixed factorial ANOVA to examine interaction effects between group (AET, SC, and HC) and time (pre- and post-) on measures of ERP, balance, BDNF and reaction time. If an interaction is found between group and time on any of the dependent variables (ERP, balance, BDNF and reaction time), the interaction will be explained using simple main effects. If no interaction is found for any of the dependent variable measures, the main effects for time and groups will be examined by a post hoc analysis to determine differences between groups. We anticipate greater change in the AET group compared to SC and HC group.

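### Healthy controls are neither matched nor adjusted for age and sex, so single-time comparisons with them and the fallback group main effect may be confounded; AET versus SC is not affected

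*Combined protocol and SAP*

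**What the plan says.** - **Who is randomised.** Section 5.1: "PCS participants will be randomly assigned to either an AET or standard of care (SC) intervention". For the third group: "Healthy participants will serve as the control group (HC) and will receive no treatment".
- **What is balanced.** Section 5.1 says that "each intervention group will be balanced by age and sex". Section 6.4 confirms that minimisation is the step that assigns a person to an intervention group, so HC never pass through it.
- **Where HC come from.** Section 6.1 opens its account with "In order to recruit healthy participants, and to reach the general public" and goes on to the School of Kinesiology's Facebook and Twitter pages, with posters around the university and in public places in the city. An interested healthy person responds directly: "he/she will contact the research team using the contact information on the recruitment posters". Flyers aimed at PCS participants go to a physiotherapy office and other clinics. A PCS candidate is routed through a clinician: "he/she will be referred by his/her healthcare provider, or referred by his/her self to" that clinician.
- **Who can be HC.** Section 4.2 and the HC checklist in 16.3 set an age range of 18 to 50. There is no matching rule and no age or sex quota.
- **How HC are used.** Section 11.2 fits a mixed ANOVA with three groups and two times to ERP, balance, BDNF and reaction time, and names no covariate. If there is no interaction, it examines main effects, including group. It closes with "We anticipate greater change in the AET group compared to SC and HC group". Section 10 uses the same three groups for driving reaction time. Hypothesis 2 in section 2 expects the AET-HC difference in neural processing to be smaller after the intervention than before.
- **Why age could matter.** Section 1 states that "it is known that executive function and circulating BDNF both decline with age".

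**The concern.** The plan treats age and sex as important enough to balance between the two randomised groups, where randomisation already protects on average. It leaves them uncontrolled in the one comparison that randomisation does not protect. HC serve as the benchmark for normal function, and they are drawn largely through different channels from the PCS participants.

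If HC happen to differ in age or sex mix, a PCS-HC difference in BDNF, ERP or reaction time at one time point is partly a demographic difference. The same holds for the group main effect. Under hypothesis 2, a gap that remains after treatment could be read as incomplete recovery when it is an age difference, or a closed gap could be read as a return to normal when it is not.

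**Working it through.** The plan gives no figure on this point to reproduce: no age distribution, no age-outcome correlation and no expected HC difference. The check has two parts.

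**1. Which contrasts can carry an age or sex offset**

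Let c be the part of the mean difference between a PCS group and HC that is due to age or sex, assumed constant over eight weeks. Let d_pre and d_post be the differences due to concussion and its treatment.

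| Contrast | What is estimated | Effect of c |
|---|---|---|
| AET vs SC | Randomised, minimised on age and sex | None |
| PCS group vs HC, one time | d_pre + c, or d_post + c | All of c |
| Group main effect with HC (11.2 fallback) | (d_pre + d_post)/2 + c | All of c |
| Group x time; narrowing under hypothesis 2 | (d_post + c) - (d_pre + c) = d_post - d_pre | Cancels |
| Gap remaining after treatment (reading of hypothesis 2) | d_post + c | All of c |

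The interaction is biased only if c changes between pre and post, that is, if age or sex alters the eight-week course, for example through practice effects on the tasks.

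**2. How large c might be (illustration)**

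Input from the documents: 20 per group (5.2) and ages 18 to 50 (4.2).

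Assumptions not in the documents:
- Within-group age SD of 9.24 years, the SD of a uniform spread over the allowed range: (50 - 18)/sqrt(12) = 32/3.464 = 9.24. This is only a scale. Two groups that both filled the range uniformly would have the same mean, and the gap would be 0.
- Mean age gap g between HC and a PCS group of 0 to 10 years.
- Age-outcome correlation r of 0.2 to 0.5.

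The planned ANOVA is unadjusted, so the bias is expressed in total-SD units: bias = r x g / 9.24. For example, 0.5 x 10 / 9.24 = 0.54. In brackets is the two-sided false-positive rate at nominal 5% for a single-time HC contrast with no true difference, 20 vs 20 (noncentral t, 38 df, noncentrality = bias x sqrt(10)).

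| g (years) | r = 0.2 | r = 0.3 | r = 0.5 |
|---|---|---|---|
| 0 | 0 (5%) | 0 (5%) | 0 (5%) |
| 3 | 0.06 (5.5%) | 0.10 (6.0%) | 0.16 (7.9%) |
| 5 | 0.11 (6.3%) | 0.16 (7.9%) | 0.27 (13.3%) |
| 10 | 0.22 (10.2%) | 0.32 (17.0%) | 0.54 (38.5%) |

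**3. What adjustment would cost**

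For a two-group contrast with HC, adjusting for age multiplies the variance by 1 + (g/9.24)^2/4. This is 1.03, 1.07 and 1.29 for g = 3, 5 and 10. At g = 10 the interval is wider by a factor of sqrt(1.29) = 1.14. That is before allowing for the residual variance that age removes (a factor of 1 - r^2): at r = 0.5 the net factor is 1.29 x 0.75 = 0.97, and at r = 0.2 it is 1.29 x 0.96 = 1.24.

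**The case against.** Several stronger readings are tempting, and the documents do not support them.

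- **That the HC comparisons are confounded.** The documents show that age and sex are uncontrolled for HC, not that they are imbalanced. Both populations share the 18 to 50 limits.
- **That HC will be young students.** Section 6.1 also puts posters in public places and states the aim of reaching the general public. Section 4.1 describes flyers and social media for participants in general, so the sources differ without being wholly separate. Nor does self-referral separate the groups, since PCS candidates may refer themselves too.
- **That the treatment effect is compromised.** AET versus SC is randomised and balanced on both factors. Only hypothesis 2 names HC as a comparator: hypothesis 5 is against SC, and hypotheses 1, 3 and 4 name no HC comparison.
- **That narrowing of the AET-HC gap loses its meaning.** Narrowing is a group-by-time contrast, and a constant offset cancels from it. What suffers is the interpretation of the gap that remains.
- **That the protocol's own age statement proves the point.** It concerns circulating BDNF and executive function, whereas the trial assays saliva. It says nothing on sex, ERP amplitude or driving reaction time. The case for sex rests only on its use as a minimisation factor.
- **That the bias could reach 0.62 SD.** That figure comes from dividing 0.54 by sqrt(1 - 0.25), which standardises by the age-adjusted residual SD. The planned analysis is unadjusted, so the total-SD scale applies.

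All of this limits the scope of the point. What it does not answer is that no section provides matching or adjustment, while 11.2 prespecifies a group main effect that includes HC.

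**Conclusion.** The point holds in a limited form, as an inexpensive improvement rather than a flaw in the trial's main evidence. Three things are exposed to possible confounding by age or sex: single-time contrasts with HC, the fallback group main effect in 11.2, and the reading of the remaining AET-HC gap under hypothesis 2. The randomised AET versus SC contrast is not exposed. The group-by-time interaction is exposed only if age or sex changes the eight-week trajectory.

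The size is unknown. Under the stated assumptions the single-time bias runs from 0 to 0.54 SD (0.11 to 0.54 SD if the mean age gap is 5 to 10 years). The upper end needs both a 10-year gap and a correlation of 0.5, and nothing in the documents establishes either.

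**What to change.** In section 11.2, state that every model that includes HC carries age (continuous) and sex as covariates, and adds age-by-time and sex-by-time terms wherever change is compared with HC. Apply the same to the driving and ERP analyses in section 10. State also that the conclusion on the effect of AET rests on AET versus SC, with HC as a descriptive benchmark.

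**Cost.** No new data: age and sex are already recorded (8.1 and the data abstraction form in 16.4). With 60 participants in three groups, the error degrees of freedom fall from 60 - 3 = 57 to 55 with two covariates, both between participants and, with the time interactions, within participants. Intervals on HC contrasts become slightly wider if ages differ, by the factors shown in the working. Prespecifying the covariates now also avoids choosing them after the data are seen.

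**Optional.** In section 6.1, monitor HC enrolment so that its age and sex mix roughly follows that of the PCS participants. This keeps the adjustment from relying on extrapolation between groups of different ages. HC recruitment would have to trail PCS recruitment a little, and some volunteers might be turned away. Sections 5.1, 6.4 and 12.2 state no age categories for the minimisation, so any formal matching rule would have to define its own.
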